10.5 Replacement of Subjects

Subjects who withdraw or are withdrawn for nonsafety reasons during the study drug treatment periods may be replaced at Vertex's discretion.

11 STUDY DRUG ADMINISTRATION AND MANAGEMENT

11.1 Preparation and Dispensing

Study drug may be dispensed only under the supervision of the investigator or an authorized designee and only for administration to the study subjects.

11.2 Administration

On Day 1 of Part A, subjects who meet all inclusion and exclusion criteria will receive a single dose of 25-mg, 50-mg, or 75-mg ivacaftor (or other dose, based on emerging PK data; dose by weight, see Section 9.3.2) in the clinic. Each dose of granules will be mixed with approximately 1 teaspoon (5 mL) of appropriate liquid or soft food (as listed in the study manual) and administered with an age-appropriate fat-containing meal or snack. All subjects will be observed for 4 hours after administration of the first dose of study drug.

In Part A, doses administered from the evening dose on Day 1 through the evening dose on Day 3 will be administered q12h at home, and the Day 1 and Day 4 morning dose will be administered in the clinic. Parents will be instructed on how to empty the packet and administer ivacaftor with food or liquid. Details of dose preparation and dose administration will be provided in the study manual. A diary of the dose administration dates and times, occurrence and time of regurgitation within 1 hour after dosing, and whether doses were administered with food during the 3 days will be kept by the subject's parents/caregivers.

On Day 1 of Part B, subjects who meet all inclusion and exclusion criteria will receive a single dose of 25-mg, 50-mg, or 75-mg ivacaftor, or other suitable starting dose based on PK data from Part A (by weight, see Section 9.3.2) in the clinic; all subjects will be observed for 4 hours after administration of the first dose of study drug. Each dose of granules will be mixed with approximately 1 teaspoon (5 mL) of appropriate liquid or soft food (as listed in the study manual) and administered orally q12h with an age-appropriate fat-containing meal or snack from Day 1 through Week 24. Details of dose preparation and dose administration will be provided in the study manual.

At the Part B Week 2, Week 8, and Week 24 Visits, the administration dates and timing with respect to food intake and occurrence and time of regurgitation within 1 hour after dosing for the 2 doses of study drug administered immediately prior to the study visit should be recorded in each subject's dosing diary. In addition, the time of administration of study drug and occurrence and time of regurgitation within 1 hour after dosing in clinic on the day of the visit will be recorded.

On Day 1 of Part A/B Cohort 8, subjects who meet all inclusion and no exclusion criteria will receive a single dose of 5.7 mg or 11.4 mg ivacaftor based on Day 1 age and weight (see Section 9.3.2) in the clinic. Each dose of granules will be mixed with approximately 1 teaspoon (5 mL) of appropriate liquid or soft food (as listed in the study manual) and administered with an age-appropriate fat-containing meal or snack. All subjects will be observed for 4 hours after administration of the first dose of study drug.

In Part A/B Cohort 8, doses from the evening dose on Day 1 through the evening dose on Day 14 will be administered q12h at home, except for the Day 4 morning dose, which will be administered in the clinic. Parents will be instructed on how to empty the packet and administer ivacaftor with food or liquid. Details of dose preparation and dose administration will be

provided in the study manual. A diary of the dose administration dates and times, occurrence and time of regurgitation within 1 hour after dosing, and whether doses were administered with food/liquid during the 3 days prior to the Day 4 Visit, will be kept by the subject's parents/caregivers. If regurgitation of a dose should occur, the subject should not be re-dosed

At the Day 15 Visit of Part A/B Cohort 8, the ivacaftor dose will be adjusted, if necessary, to 5.7, 11.4, 17.1, 22.8, or 25 mg based on PK data from Day 4 (see Section 9.3.2), and the adjusted dose will be administered starting with the evening dose on Day 15. The subject should then remain on the same dose from Day 15 until the subject is 4 months of age and at least 5 kg, after which the recommended age- and weight-appropriate dose(s) will be administered.

Each dose of granules will be mixed with approximately 1 teaspoon (5 mL) of appropriate liquid or soft food (as listed in the study manual) and administered orally q12h with an age-appropriate fat-containing meal or snack from the evening dose on Day 15 through Week 24. Aside from doses administered during scheduled clinic visits, doses from the evening dose on Day 15 through Week 24 will be administered q12h at home. Details of dose preparation and dose administration will be provided in the study manual.

At the Part A/B Cohort 8 Week 4, 8, 12, 18, and 24 Visits, the dose administration dates and times, occurrence and time of regurgitation within 1 hour after dosing, and whether doses were administered with food/liquid will be recorded for the 2 doses of study drug administered immediately prior to each PK clinic visit in each subject's dosing diary. In addition, the time of administration of study drug and occurrence and time of regurgitation within 1 hour after dosing in clinic on the day of the visit will be recorded.

When possible, subjects should take the dose of ivacaftor at the same time each day. If the caregiver of the subject forgets to administer a dose and remembers within 0 to 6 hours (before the halfway point of the dosing interval), the subject should be given the dose at that time and resume their normal schedule for the following dose. If caregiver of the subject forgets to give a dose and remembers within 6 to 12 hours after the missed dose, they should skip that dose and resume their normal schedule for the following dose.

11.3 Method of Assigning Subjects to Treatment Groups

This study is open-labeled and all subjects will receive ivacaftor.

11.4 Dose Modification for Toxicity

The investigator may interrupt study drug dosing if medically necessary. If study drug dosing must be interrupted for more than 72 hours, the Vertex medical monitor must be notified. In these instances, study drug dosing may only resume after approval by the Vertex medical monitor. Specific instructions for interruption for elevated LFT levels are provided in Section 12.6.2.

11.5 Packaging and Labeling

Ivacaftor granules in a foil-laminated sachet/packet will be supplied by Vertex in kits. Study drug labeling will be in compliance with applicable local and national regulations. Additional details regarding packaging, labeling, and dispensing for ivacaftor will be included in the pharmacy manual.

11.6 Study Drug Supply, Storage, and Handling

The investigator, or an authorized designee (e.g., a licensed pharmacist), will ensure that all investigational product is stored in a secured area, under recommended storage conditions, and in accordance with applicable regulatory requirements. To ensure adequate records, all study drugs will be accounted for as described in Section 11.7. Study drug must be stored at temperatures of $\leq 25^{\circ}\text{C}$ (77°F) with excursions to 30°C (86°F). Additional storage and handling conditions will be provided in the pharmacy manual.

11.7 Drug Accountability

The pharmacist or designated study site staff will maintain information regarding the dates and amounts of (1) study drug received, (2) study drug dispensed to the subjects, and (3) study drug returned by the subjects' parent or legal guardian. Subjects' parent or legal guardian will be instructed to return all used and unused materials associated with the study drug to the site. These materials will be retained at the site according to instructions provided by Vertex or its designee until inventoried by the study monitor. The study monitor will review study drug records and inventory throughout the study.

11.8 Disposal, Return, or Retention of Unused Drug

The study site staff or pharmacy personnel will retain all materials returned by the subjects' parent or legal guardian until the study monitor has performed drug accountability. At the end of the study, the study monitor will provide instructions as to the disposition of any unused investigational product. If the study monitor authorizes destruction at the study site, the investigator will ensure that the materials are destroyed in compliance with applicable environmental regulations, institutional policy, and any special instructions provided by Vertex. Destruction will be adequately documented.

11.9 Compliance

Study drug accountability should be assessed at each visit by counting returned dosage units (sachets/packets).

If there is continued non-compliance with study requirements, restrictions, instructions, and study drug dosing despite educational efforts, the investigator should contact the Vertex medical monitor to discuss noncompliance and discontinuation of the subject from the study.

11.10 Blinding and Unblinding

This will be an open-label study.

12 ASSESSMENTS

12.1 Timing of Assessments

The timing of assessments is shown in:

- [Table 3-1](#) for Part A (Screening, Treatment, ETT, and Follow-up Periods)
- [Table 3-2](#) for Part B (Screening and Treatment Periods)
- [Table 3-3](#) for Part B (ETT Visit and Follow-up Periods)
- [Table 16-1](#) for Part A/B Cohort 8 (Screening, Treatment, ETT, and Follow-up Periods)

12.2 Subject and Disease Characteristics

Subject and disease characteristics include demographics and medical history. In addition, the following historical data will be collected for each Part B and Part A/B Cohort 8 subject from birth to screening: age at CF diagnosis, [REDACTED] pulmonary exacerbations, LFTs, and CF-related medications-of-interest. The following historical data from birth to screening will also be collected:

- Maternal/pregnancy history: complications in pregnancy, gestational age at delivery, method of delivery
- Quarterly (approximately every 12 weeks) [REDACTED]
- The dates and reasons for all [REDACTED]
- Any use (yes or no) of the following medications will be assessed: inhaled tobramycin, inhaled aztreonam, inhaled colimycin, inhaled hypertonic saline, dornase alfa, ibuprofen, azithromycin, and pancreatic enzyme replacement therapy.
- Historical pancreatic status measurements

12.3 Pharmacokinetics

12.3.1 Blood Sampling

At visits indicated in Part A [Table 3-1](#), Part B [Table 3-2](#) and [Table 3-3](#), and Part A/B Cohort 8 [Table 16-1](#), blood samples will be collected for the determination of the concentrations of ivacaftor and metabolites M1 and M6 in plasma. Approximately 0.25 mL of blood will be collected at each PK time point.

PK blood sampling time points are relative to the morning dose of study drug. The sampling schedule is as follows:

Part A

- Day 4: before the morning dose; between 2 and 4 hours and between 6 and 8 hours after the Day 4 morning dose
- Day 5: between 24 and 60 hours after the Day 4 morning dose.
- For subjects who prematurely discontinue treatment, a PK blood sample will be collected at the ETT Visit.
- The administration dates and times and their timing with respect to food intake of all study drug doses administered outside the clinic should be recorded in each subject's dosing diary.

Part B

- Week 2: before the morning dose, between 2 and 4 hours and between 6 and 8 hours after the morning dose
- Week 8: before the morning dose and 1 and 4 hours after the morning dose
- Week 24: before the morning dose and between 2 and 4 hours after the morning dose
 - PK blood sampling at Week 24 is optional for subjects who undergo MBW (due to fasting requirements)

- For subjects who prematurely discontinue treatment, a PK blood sample will be collected at the ETT Visit.
- The dose administration dates and times, and their timing with respect to food intake, will be recorded for the 2 doses prior to each PK clinic visit in each subject's dosing diary.

Part A/B Cohort 8

- Day 4: before the morning dose; between 2 to 4 hours and between 6 to 8 hours after the Day 4 morning dose
- Day 15: before the morning dose
- Weeks 4, 12, 18 and 24: before the morning dose
- Week 8: before the morning dose; between 2 to 4 hours and between 6 to 8 hours after the Week 8 morning dose
- For subjects who prematurely discontinue treatment, a PK blood sample will be collected at the ETT Visit only if within 3 days of last dose of study drug.
- The dose administration dates and times, occurrence and time of regurgitation within 1 hour after dosing, and whether doses were administered with food/liquid will be recorded for the 2 doses of study drug administered immediately prior to each PK clinic visit in each subject's dosing diary.

The total anticipated blood volume collected at each study visit is presented in [Table 12-1](#).

Cumulatively, each subject is expected to have 27.0 mL of blood collected over the course of the study (from Screening to Week 24), excluding the ETT. The total blood volume collected at any single study visit is not expected to exceed about 1% of a subject's estimated total blood volume (based on body weight) and the total blood volume collected over the course of any 4 weeks is not expected to exceed about 3% of a subject's estimated blood volume. Total blood volume was estimated based on the expectation of total volume being at least 80 mL blood/kg body weight (240 mL at Day 1 for a subject weighing 3 kg).⁹³

Table 12-1 Expected Blood Volumes to be Collected at Each Study Visit

Study Visit	Assessments Requiring Blood Collection	Total Blood Volume (mL)
Screening (Day -28 to -14)	Serum chemistry, Hematology	2.3
Day 1	Serum chemistry, IRT	2.2
Day 4	Serum chemistry, PK ^a	2.6
Day 15	Serum chemistry, Hematology, PK ^a	2.8
Week 4	Serum chemistry, Hematology, PK ^a	2.8
Week 8	Serum chemistry, PK ^a	2.6
Weeks 12, 18, and 24	Serum chemistry, Hematology, PK ^a , IRT	3 × 3.9 = 11.7
ETT	Serum chemistry, Hematology, PK ^b	2.8

ETT: Early Termination of Treatment; IRT: immunoreactive trypsin and/or trypsinogen; PK: pharmacokinetic

^a PK samples will be collected before the morning dose and between 2 to 4 hours and between 6 to 8 hours after the morning dose on Day 4 and Week 8. PK samples will be collected before the morning dose on Day 15, and on Weeks 4, 12, 18, and 24.

^b PK sample will be collected only if within 3 days of last dose of study drug.

The acceptable windows for the PK sampling time points are listed in [Table 12-2](#). Samples collected outside these acceptable windows will be considered protocol deviations. All efforts will be made to obtain the PK samples at the exact nominal time relative to dosing.

Table 12-2 Acceptable Pharmacokinetic Sampling Windows

Study Part	Nominal Sampling Times	Acceptable Window
Part A	ETT Visit	at the time of the ETT Visit
	Day 4: 0 (before morning dose)	within 60 minutes before dosing
	Day 4: between 2 and 4 hours after the Day 4 morning dose	within the time window of 2 to 4 hours after the Day 4 morning dose
	Day 4: between 6 and 8 hours after the Day 4 morning dose	within the time window of 6 to 8 hours after the Day 4 morning dose
	Day 5: 24 and 60 hours after the Day 4 morning dose	within the time window of 24 to 60 hours after the Day 4 morning dose
Part B	ETT Visit	at the time of the ETT Visit
	Week 2: 0 (before morning dose)	within 60 minutes before dosing
	Week 2: between 2 and 4 hours after the morning dose	within the time window of 2 and 4 hours after the morning dose
	Week 2: between 6 and 8 hours after the morning dose	within the time window of 6 and 8 hours after the morning dose
	Week 8: 0 (before morning dose)	within 60 minutes before dosing
	Week 8: 1 and 4 hours after the morning dose	± 15 minutes
	Week 24: 0 (before morning dose)	within 60 minutes before dosing
Part A/B Cohort 8	ETT Visit ^a	at the time of the ETT Visit
	Day 4: 0 (before morning dose)	within 60 minutes before dosing
	Day 4: between 2 and 4 hours after the Day 4 morning dose	within the time window of 2 to 4 hours after the Day 4 morning dose
	Day 4: between 6 and 8 hours after the Day 4 morning dose	within the time window of 6 to 8 hours after the Day 4 morning dose
	Day 15, Weeks 4, 12, 18, and 24: 0 (before morning dose)	within 60 minutes before dosing
	Week 8: 0 (before morning dose)	within 60 minutes before dosing
	Week 8: between 2 and 4 hours after the Week 8 morning dose	within the time window of 2 to 4 hours after the Week 8 morning dose
	Week 8: between 6 and 8 hours after the Week 8 morning dose	within the time window of 6 to 8 hours after the Week 8 morning dose

^a Assessment will be performed only if within 3 days of last dose of study drug.

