- ^k To minimize the volume of blood drawn on Day 1, clinical laboratory assessments will be determined from a single blood draw taken during the Screening Period Day -28 to Day -14. The results must be received and reviewed before the first dose of study drug. All blood samples will be collected while subjects are in a seated or supine position.
- ^l PK samples will be collected before the morning dose and between 2 to 4 hours and between 6 to 8 hours after the morning dose on Day 4 and the Week 8 Visit. PK samples will be collected before the morning dose on Day 15, and on the Week 4, 12, 18, and 24 Visits.
- ^m If all PK samples collected on Day 4 are missing or cannot be analyzed, PK samples collected on Day 15 will be used to assess whether the initial dose should be adjusted at the Week 4 Visit.
- ⁿ Assessment will be performed only if within 3 days of last dose of study drug.
- ^o At Screening a sweat chloride test must be performed if the sweat chloride value is not available in the subject's medical records and the value is needed to establish eligibility. For subjects with sweat chloride values documented in their medical records and for whom it is not needed to establish eligibility, the sweat chloride test at screening is not required. At the Day 1 Visit, the sweat chloride test must be performed before the morning dose. At the Day 15 and Week 4, 8, 12, 18 and 24 Visits, the sweat chloride test must be performed within a window of ± 2 hours relative to the morning dose of the study drug.
- [REDACTED]

Table 3-4 Study VX15-770-124: Part A/B Cohort 8 (Screening, Treatment, Early Termination of Treatment, and Follow-up Periods)

Event/Assessment	Screening Period	Treatment Period (Day 1 to Week 24)							Early Termination of Treatment Visit ^a	Follow-up Visit ^b	Follow-up Ophthalmologic Examination ^c
	Day -28 to Day -14	Day 1	Day 4	Day 15 (± 1 Day)	Day 17 (± 1 Day)	Week 4 (± 5 Days)	Week 8 (± 5 Days)	Weeks 12, 18, and 24 (± 5 Days)	As Soon as Possible After the Last Dose of Study Drug	4 Weeks (± 7 Days) After Last Dose of Study Drug	12 Weeks (± 14 Days) After Last Dose of Study Drug
In-clinic observation for 4 hours after administration of the first dose of study drug		X									
Study drug count		X		X		X	X	X	X		
Study drug dispensing		X		X		X	X	X ^r			
Adverse events	Continuous from signing of ICF through ETT and Follow-up Visit (if required; see Section 14.1.1.3)									Ocular adverse events only	

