All subjects must have gestational age ≥38 weeks and weigh ≥3 kg. Subjects 3 months of age must weigh ≥5 kg on Day 1.

On Day 4, PK samples from each subject will be collected before and after dosing and analyzed to determine the exposure and assess whether the initial dose needs to be adjusted to better match the median adult exposure. The ivacaftor dose will be adjusted (if necessary) to either 5.7, 11.4, 17.1, 22.8, or 25 mg, and the adjusted dose will be communicated in writing to the principal investigator to administer to the subject on Day 15. The subject should then remain on the same dose of ivacaftor from Day 15 until the subject is 4 months of age and at least 5 kg, after which the recommended age- and weight-appropriate dose(s) will be administered.

If all PK samples collected on Day 4 are missing or cannot be analyzed, PK samples collected on Day 15 will be used to assess whether the initial dose should be adjusted at the Week 4 Visit.

The entire treatment period of the study will be 24 weeks, after which subjects will be eligible to enroll in an Extension Study and receive open-label ivacaftor treatment. The 24-week treatment period will provide subject data at least through the age of 7 months.

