10.1 Inclusion Criteria

Subjects who meet all of the following inclusion criteria will be eligible.

1. Male or female with confirmed diagnosis of CF, defined as a sweat chloride value ≥ 60 mmol/L by quantitative pilocarpine iontophoresis OR 2 CF-causing mutations.
 - A sweat chloride test must be performed if the sweat chloride value is not available in the subject's medical records and the value is needed to establish eligibility. For subjects with sweat chloride values documented in their medical records and for whom it is not needed to establish eligibility, the sweat chloride test at screening is optional.
2. Have 1 of the following 9 *CFTR* mutations on at least 1 allele: *G551D*, *G178R*, *S549N*, *S549R*, *G551S*, *G1244E*, *S1251N*, *S1255P*, or *G1349D*. Subjects who have an *R117H-CFTR* mutation will be eligible in regions where ivacaftor is approved for use in subjects with an *R117H-CFTR* mutation. Subjects eligible for Part A/B Cohort 8 may also have other ivacaftor-responsive mutations (see Appendix A).
 - If a genotype test has been performed previously and is documented in the subject's medical record, the subject's eligibility must be approved by the Vertex medical monitor (see Section 12.6.2). If a historic genotype result is not available at screening or if the historic genotype result is not approved by the Vertex medical monitor, the subject will be tested for *CFTR* genotype at screening and the results must be reviewed before the first dose of ivacaftor. Subjects who have been enrolled and whose screening genotype does not confirm study eligibility will not receive study drug.
 - Subjects who have an ivacaftor-responsive mutation on at least 1 allele will be eligible to enroll in Part A/B Cohort 8 in regions where ivacaftor is approved (consistent with the approved mutations in the region; see Appendix A).
 - Subjects must be ≥ 1 to < 4 months of age, ≥ 38 weeks gestation, and weigh ≥ 3 kg at Day 1 (treatment initiation); subjects 3 months of age must weigh ≥ 5 kg on Day 1 (Section 9.3.2)
 - Subjects must have a documented genotype test (performed to applicable national standards). Genotype testing is expected to be initiated prior to screening. Results of the genotype test are to be reviewed and approved by the Vertex medical monitor prior to Day 1.
 - Subjects with the *R117H* genotype should have the 5T variant or a sweat chloride value ≥ 60 mmol/L by quantitative pilocarpine iontophoresis.

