# Appendix D: Analysis Visit Window Mapping Rules for Safety and Efficacy Assessments

**Table 11-4 Analysis Visit Windows for Safety Assessments for Part B** 

Safety Assessment	Visit a	Target Study Day	Analysis Visit Window (in study days)
Serum Chemistry	Baseline	1	≤1
	Week 2	14	[2,35]
	Week 8	56	[36,70]
	Week 12	84	[71,105]
	Week 18	126	[106,147]
	Week 24	168	[148, Date of Week 24 Visit]
	Follow-up Visit	NA	Use nominal visit
LFTs	Baseline	1	≤1
	Week 2	14	[2,21]
	Week 4	28	[22,42]
	Week 8	56	[43,70]
	Week 12	84	[71,105]
	Week 18	126	[106,147]
	Week 24	168	[148, Date of Week 24 Visit]
	Follow-up Visit	NA	Use nominal visit
Hematology	Baseline	1	≤1
	Week 4	28	[2,42]
	Week 8	56	[43,70]
	Week 12	84	[71,105]
	Week 18	126	[106,147]
	Week 24	168	[148, Date of Week 24 Visit]
	Follow-up Visit	NA	Use nominal visit
Standard 12-Lead ECG	Baseline	1	≤1
	Week 4	28	[2,56]
	Week 12	84	[57,126]
	Week 24	168	[127, Date of Week 24 Visit]
Vital Signs	Baseline	1	≤1

	Week 2	14	[2,21]
	Week 4	28	[22,42]
	Week 8	56	[43,70]
	Week 12	84	[71,105]
	Week 18	126	[106,147]
	Week 24	168	[148, Date of Week 24 Visit]
	Follow-up Visit	NA	Use nominal visit
Ophthalmologic Exam	Baseline	1	≤1
	Week 12	84	[2,126]
	Week 24	168	[127, Date of Week 24 Visit]
	Follow-up OE visit	NA	Use nominal visit

When a subject is lost to follow up and last dose date is unknown, impute last dose date of all study drugs as last on-treatment visit date.

<sup>aVisit name is used to report data in tables, listings and figures.

Table 11-5 Analysis Visit Windows for Efficacy Assessments for Part B

Safety Assessment	Visit a	Target Study Day	Analysis Visit Window (in study days)
	Follow-up Visit	NA	Use nominal visit
weat Chloride	Baseline	1	≤1
	Week 2	14	[2,49]
	Week 12	84	[50,126]
	Week 24	168	[127, Date of Week 24 Visit]

When a subject is lost to follow up and last dose date is unknown, impute last dose date of all study drugs as last on-treatment visit date.

aVisit name is used to report data in tables, listings and figures.

Table 11-6 Analysis Visit Windows for Safety Assessments for Part A/B Cohort 8

Safety Assessment	Visit a	Target Study Day	Analysis Visit Window (in study days)	
Serum Chemistry	Baseline	1	≤1	
	Day 4	4	[2,9]	
	Day 15	15	[10,21]	
	Week 4	28	[22,42]	
	Week 8	56	[43,70]	
	Week 12	84	[71,105]	
	Week 18	126	[106,147]	
	Week 24	168	[148, Date of Week 24 Visit]	
	Follow-up Visit	NA	Use nominal visit	
Hematology	Baseline	1	≤1	

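### Table 12-1 implies 0.50 mL per PK sample against about 0.25 mL in the text, and its Day 1 to Week 4 draws reach 4.33% of blood volume in a 3-kg infant against a stated expectation of about 3%

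*Protocol*

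**What the plan says.** Protocol Section 12.3.1 makes these statements about blood volume:

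- PK sample size: "Approximately 0.25 mL of blood will be collected at each PK time point".
- Study total: "each subject is expected to have 27.0 mL of blood collected over the course of the study", from Screening to Week 24 and excluding the early termination visit.
- Four-week total: "the total blood volume collected over the course of any 4 weeks is not expected to exceed about 3"% of estimated blood volume. A companion statement puts any single visit at no more than about 1%.
- Basis: "the expectation of total volume being at least 80 mL blood/kg body weight", with 240 mL given as the value for a 3-kg infant on Day 1.

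Table 12-1 then lists the volume at each visit of the Cohort 8 schedule. Section 10.1 requires Cohort 8 infants to "weigh ≥ 3 kg at Day 1 (treatment initiation"). Section 9.3.2 adds "Subjects 3 months of age must weigh ≥5 kg on Day 1", so only 1- and 2-month-olds can enter between 3 and 5 kg.

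Table 3-4 allows ±5 days around Week 4, and SAP Appendix D ("Table 11-6 Analysis Visit Windows for Safety Assessments for Part A/B Cohort 8") sets its target at study day 28. The Table 3-4 grid and Table 12-1 both show serum chemistry on Day 1. Footnote k of Table 3-4, however, says that "clinical laboratory assessments will be determined from a single blood draw taken during the Screening Period", with the aim of limiting the Day 1 draw.

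**The concern.** Two statements in Section 12.3.1 do not fit the table beneath them. The table appears to use twice the PK volume given in the text. Its first four treatment-period visits also add up to more than the 4-week figure for an infant at the eligibility floor.

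This is the blood-loss expectation that ethics committees read for infants aged 1 to <4 months. The protocol treats it as a real constraint: Section 9.1.1 places screening at least 14 days before Day 1 to limit blood drawn in a 28-day span. If the 4-week figure is wrong for the lightest infants, the document understates their expected blood loss. If instead the table is wrong, the per-visit volumes and the study total are overstated.

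**Working it through.** **Inputs (Table 12-1, mL).** Screening 2.3 (chemistry, hematology); Day 1 2.2 (chemistry, IRT); Day 4 2.6 (chemistry, 3 PK); Day 15 2.8 and Week 4 2.8 (chemistry, hematology, 1 PK each); Week 8 2.6 (chemistry, 3 PK); Weeks 12, 18 and 24 3.9 each (chemistry, hematology, 1 PK, IRT).

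**1. The plan's total reproduces.** 2.3 + 2.2 + 2.6 + 2.8 + 2.8 + 2.6 + 11.7 = 27.0 mL, as stated.

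**2. PK volume implied by the table.** Day 15 is Screening plus one PK sample, so PK = 2.8 − 2.3 = 0.50 mL. Solving the seven distinct visit rows for four component volumes gives chemistry 1.1, hematology 1.2, IRT 1.1 and PK 0.50, with no residual. Two checks:

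- Day 4: 1.1 + 3 × 0.50 = 2.6
- Week 12: 1.1 + 1.2 + 0.50 + 1.1 = 3.9

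Rounding does not explain the gap from 0.25. If each entry is within ±0.05, the Day 15 minus Screening difference lies between 2.75 − 2.35 = 0.40 and 2.85 − 2.25 = 0.60 mL. There are 11 PK samples in all (3 + 1 + 1 + 3 + 1 + 1 + 1), so at 0.25 mL the total would be 27.0 − 11 × 0.25 = 24.25 mL.

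**3. Day 1 to Week 4.** 2.2 + 2.6 + 2.8 + 2.8 = 10.4 mL. With Week 4 at Day 28 ± 5, the visit may fall on Days 23 to 33. On Days 23 to 28, which are 6 of those 11 days and include the target, all four draws lie within 28 days.

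**4. As a share of blood volume.** Percent = volume / (80 × weight) × 100, at Day 1 weight, for the tabulated 10.4 mL:

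| Weight (kg) | Percent |
|---|---|
| 3.0 | 10.4/240 = 4.33 |
| 3.5 | 10.4/280 = 3.71 |
| 4.0 | 10.4/320 = 3.25 |
| 5.0 | 10.4/400 = 2.60 |

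**5. Weight below which the figure is exceeded.** Weight = volume / (80 × limit). At a literal 3% this is 10.4/2.4 = 4.33 kg. The protocol does not define *about*. Its single-visit statement tolerates 2.8/240 = 1.17% as about 1%, and the same latitude gives 3 × 1.17% = 3.5%. At 3.5% the cut-off is 10.4/2.8 = 3.71 kg.

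**6. Alternative readings of the inputs, Week 4 by Day 28.** Five PK samples fall between Day 1 and Week 4, so moving from 0.50 to 0.25 mL removes 5 × 0.25 = 1.25 mL. Omitting Day 1 chemistry removes 1.1 mL.

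| Reading | mL | Percent at 3 kg | Exceeds 3.5% below |
|---|---|---|---|
| As tabulated | 10.4 | 4.33 | 3.71 kg |
| No Day 1 chemistry | 9.3 | 3.88 | 3.32 kg |
| PK at 0.25 mL | 9.15 | 3.81 | 3.27 kg |
| Both changes | 8.05 | 3.35 | 2.88 kg (no eligible infant) |

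**The case against.** The strongest reply is that the excess depends on the calendar. If Week 4 falls after Day 28, Day 1 and Week 4 no longer share a 28-day span. The largest 28-day total from Day 1 on is then Day 4 to Week 4: 2.6 + 2.8 + 2.8 = 8.2 mL, or 3.42% at 3 kg. With 0.25 mL PK samples it is 1.85 + 2.55 + 2.55 = 6.95 mL, or 2.90%. The Day 28 target comes from an SAP table that assigns data to analysis visits. SAP Section 8.2.1 pairs Day 15 with Week 2, and on that count Week 4 would be Day 29. This stands as a condition on the finding. It does not remove it: the only stated target is Day 28, and a window of Day 29 ± 5 (Days 24 to 34) would still permit Days 24 to 28, 5 of 11 days.

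The second reply is that footnote k combined with 0.25 mL samples brings the 3-kg figure to 3.35%. That is correct, but it needs both changes at once, and two tables list Day 1 chemistry.

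The third is that the denominator is a worst case. Blood volume is put at *at least* 80 mL/kg, and infants grow. For a 3-kg infant the tabulated 10.4 mL comes down to 3.5% only if blood volume is 10.4/0.035/3 = 99 mL/kg, or if Day 28 weight is 10.4/2.8 = 3.71 kg, a gain of 0.71 kg. Under an assumed gain of 20 to 35 g/day, the total is about 3.9 to 4.0% using weight at each draw, and 3.3 to 3.7% using Day 28 weight alone. Growth therefore narrows the gap and closes it only on the most favourable choice of weight. The protocol's worked reference is the Day 1 volume at 3 kg.

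Finally, the sentence is a hedged expectation and not a stopping limit, and the scope is small. Both points are fair.

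**Conclusion.** The concern holds. The PK volume conflict, 0.50 against about 0.25 mL, is exact and needs no assumption about weight or timing. The 4-week statement fails on the protocol's own table and reference case: 4.33% at 3 kg as tabulated, and still 3.81% if only the PK volume is corrected.

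This rests on Week 4 occurring by Day 28, on Day 1 weight, and on 80 mL/kg, so the percentages are upper estimates. The 3.71-kg cut-off also assumes that about 3% extends to 3.5%; at a literal 3% the cut-off is 4.33 kg. The documents do not show whether the table or the sentence is the one in error.

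The effect is confined to the lightest 1- and 2-month-olds, since 3-month-olds enter at 5 kg or more, where the figure is 2.6%. The per-visit statement is consistent with the table over these first four weeks (at most 1.17% at 3 kg). No endpoint or analysis changes.

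**What to change.** 1. Use one PK sample volume in the Section 12.3.1 text and in Table 12-1.
2. State in Table 3-4 footnote k whether chemistry is drawn on Day 1, and align the Table 3-4 grid and Table 12-1 with the answer.
3. Recompute Table 12-1 and the 27.0 mL total (24.25 mL if only the PK volume changes, to 0.25 mL).
4. Restate the 4-week maximum for a 3-kg infant at Day 1 weight: about 4.3% as tabulated, about 3.8% with 0.25 mL samples, or about 3.4% with 0.25 mL samples and no Day 1 chemistry. In the last case the existing wording can stay.

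The per-visit statement needs no change. The cost is protocol wording and one table, with no added patients, visits or procedures; the stated 4-week figure may become less favourable. SAP Section 9.1 describes the Cohort 8 interim analysis as done after all its subjects had completed participation, so the change corrects the stated figures and not the draws themselves.
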